Appendix A. Total Bilirubin Table for Term and Preterm Neonates

PARAMETER	GRADE 1 MILD	GRADE 2 MODERATE	GRADE 3 SEVERE	GRADE 4 POTENTIALLY LIFE- THREATENING
Total Bilirubin¹⁸, High (mg/dL; $\mu\text{mol/L}$) ¹⁹				
Term Neonate²⁰ < 24 hours of age	4 to < 7 68.4 to < 119.7	7 to < 10 119.7 to < 171	10 to < 17 171 to < 290.7	≥ 17 ≥ 290.7
24 to < 48 hours of age	5 to < 8 85.5 to < 136.8	8 to < 12 136.8 to < 205.2	12 to < 19 205.2 to < 324.9	≥ 19 ≥ 324.9
48 to < 72 hours of age	8.5 to < 13 145.35 to < 222.3	13 to < 15 222.3 to < 256.5	15 to < 22 256.5 to < 376.2	≥ 22 ≥ 376.2
72 hours to < 7 days of age	11 to < 16 188.1 to < 273.6	16 to < 18 273.6 to < 307.8	18 to < 24 307.8 to < 410.4	≥ 24 ≥ 410.4
7 to 28 days of age (breast feeding)	5 to < 10 85.5 to < 171	10 to < 20 171 to < 342	20 to < 25 342 to < 427.5	≥ 25 ≥ 427.5
7 to 28 days of age (not breast feeding)	1.1 to < 1.6 x ULN	1.6 to < 2.6 x ULN	2.6 to < 5.0 x ULN	≥ 5.0 x ULN
Preterm Neonate²⁰ 35 to < 37 weeks gestational age	Same as for Total Bilirubin, High, Term Neonate (based on days of age).	Same as for Total Bilirubin, High, Term Neonate (based on days of age).	Same as for Total Bilirubin, High, Term Neonate (based on days of age).	Same as for Total Bilirubin, High, Term Neonate (based on days of age).
32 to < 35 weeks gestational age and < 7 days of age	NA	NA	10 to < 14 171 to < 239.4	≥ 14 ≥ 239.4
28 to < 32 weeks gestational age and < 7 days of age	NA	NA	6 to < 10 102.6 to < 171	≥ 10 ≥ 171
< 28 weeks gestational age and < 7 days of age	NA	NA	5 to < 8 85.5 to < 136.8	≥ 8 ≥ 136.8
7 to 28 days of age (breast feeding)	5 to < 10 85.5 to < 171	10 to < 20 171 to < 342	20 to < 25 342 to < 427.5	≥ 25 ≥ 427.5
7 to 28 days of age (not breast feeding)	1.1 to < 1.6 x ULN	1.6 to < 2.6 x ULN	2.6 to < 5.0 x ULN	≥ 5.0 x ULN

¹⁸ Severity grading for total bilirubin in neonates is complex because of rapidly changing total bilirubin normal ranges in the first week of life followed by the benign phenomenon of breast milk jaundice after the first week of life. Severity grading in this appendix corresponds approximately to cut-offs for indications for phototherapy at grade 3 and for exchange transfusion at grade 4.

¹⁹ A laboratory value of 1 mg/dL is equivalent to 17.1 $\mu\text{mol/L}$.

²⁰ Definitions: Term is defined as ≥ 37 weeks gestational age; near-term, as ≥ 35 weeks gestational age; preterm, as < 35 weeks gestational age; and neonate, as 0 to 28 days of age.

2 STUDY DESCRIPTION

2.1 Study Design

The study is an open-label, single-arm, sequential descending age cohort trial evaluating the PK profile, safety, tolerability, and efficacy of DCV+SOF, administered for 12 weeks, to paediatric participants (3 years to < 18 years), monoinfected with the hepatitis C virus (genotypes (GT) -1 to -6), who are non-cirrhotic and either treatment naive or treatment experienced.

The total duration of the study for each participant is approximately 2.5 years:

Screening Duration: 42 daysTreatment Duration: 12 weeks

• Post-Treatment Follow-up Duration: 108 weeks. Upon completion of the post-treatment follow-up Week 12 visit, participants are followed for an additional 2 years (96 weeks) as long-term follow-up to assess SVR24, durability of response, long term safety, and the persistence of resistance variants in non-responders.

A minimum of 30 participants are evaluated for the primary endpoint, with at least 8 treated per age cohort:

• Cohort 1: 12 to < 18 years old

[figure not shown]
• Cohort 2: 6 to < 12 years old

• Cohort 3: 3 to < 6 years old

Enrollment begins with Cohort 1, followed by Cohorts 2 and 3. Enrollment in Cohorts 2 and 3 is dependent on the availability of the European Commission approved SOF formulation for the corresponding age cohort.

The study design is presented in Figure 2.1-1.

Figure 2.1-1: Study Design Schematic

2.2 Treatment Assignment

All participants receive DCV+SOF in Cohort 1 (12 to < 18 years), Cohort 2 (6 to < 12 years), and 3 (3 to < 6 years). Cohorts are determined by age at Day 1 assigned by Interactive Response Technology (IRT), not age at enrollment collected on the Case Report Form (CRF).

2.3 Blinding and Unblinding

[figure not shown]
This is an open-label study; unblinding procedures are not applicable.

3 OBJECTIVES AND ENDPOINTS

Objectives and endpoints are presented in Table 3-1.

Table 3-1: Objectives and Endpoints

Objectives	Endpoints
Primary	
To evaluate the PK profile of DCV in combination with SOF in children and adolescents aged 3 to <18 years of age	 PK parameters (Cmin, Cmax, Tmax, AUC (TAU), CLT/F) for DCV derived from plasma concentration versus time data on Day 10 (± 3 days) within a dosing interval. In Cohort 3, PK parameters from model-based analyses with 5 samples from each participant.
Secondary	
To assess the safety and tolerability of the DCV+SOF regimen in pediatric participants	Frequencies of serious adverse events (SAEs), adverse events (AEs) leading to discontinuation of study therapy, AEs by intensity, and laboratory abnormalities by toxicity grade on treatment and during follow-up
To determine the proportion of participants with SVR12	Proportion of participants with HCV RNA < LLOQ (TD or TND) at post-treatment follow-up Week 12
To evaluate genotypic substitution(s) associated with virologic failure	Frequencies of NS5A and NS5B resistance-associated variants (RAVs) emergent at the time of virologic failure on treatment and during follow-up in non-responders
To assess the acceptability and palatability for the age-appropriate chewable tablet formulation, and acceptability for adult filmcoated tablet	Summary of responses from questionnaire assessing acceptability and palatability at Day 1, Week 4, and Week 12

LLOQ = lower limit of quantification; TD = target detected; TND = target not detected

4 SAMPLE SIZE AND POWER

A minimum of 30 participants, assigned to 3 age descending cohorts, are evaluated for the primary endpoint (PK) with at least 8 participants assessed in each age cohort.

The primary objective of this study is to evaluate the PK of DCV. The PK profile of DCV has been well characterized in the clinical development program and it has been noted that DCV is associated with predictable pharmacokinetics. The intra-participant variability for DCV Cmax and AUC(INF) was assessed from clinical studies where single oral doses of DCV were administered with or without food and were estimated to be low with a % CV of 18% for Cmax and 10% for AUC(INF). Similarly, the inter-participant variability in DCV Cmax and AUC were assessed from clinical studies where single and multiple oral doses of DCV administered alone, and with or without food in some cases, was identified to be modest with % CV values of 37.5% for Cmax and 35% for AUC. PK is assessed in all participants; however, due to the low observed variability in DCV exposure, assessment of the PK in the initial 5 participants per age cohort provides the necessary information to match DCV exposures between adults and paediatric participants and either allow enrollment to be initiated in the next descending age cohort(s) or indicate that additional participants need to be enrolled in the cohort with a modified dose.

Enrollment will continue in each cohort, after the initial 5 participants have completed their Day 10 assessments, to have a minimum of 8 evaluable participants in each cohort.

5 STUDY PERIODS, TREATMENT REGIMENS AND POPULATIONS FOR ANALYSES

5.1 Study Periods

Study periods are defined as follows:

- Pre-treatment period: Begins at the first screening visit and ends on the start date of study therapy (DCV or SOF).
- On-treatment period: Begins after the start date of study therapy and ends on the last date of study therapy.
- Follow-up period: Begins after the last date of study therapy.

Measurements taken before Day 1 (i.e., the start date of study therapy) are considered pretreatment for all data domains. In addition, measurements taken on Day 1 are considered pretreatment for the following data domains: demography, diagnostic procedures, disease history, ECG, human genotyping, laboratory test results (including serology and virology), medical history, physical examination, physical measurements, questionnaires, subject status, viral genotyping, viral phenotyping, and vital signs.

Measurements taken after Day 1 through the last date of study therapy are considered on-treatment for all data domains. In addition, measurements taken on Day 1 are considered on-treatment for the following data domains: AEs, drug dispensation, exposure, inclusion/exclusion, non-study medications, PK concentration, PK parameters, sample collection, sample inform consent and sample reference.

Measurements taken after the last date of study therapy are considered follow-up for all data domains unless otherwise specified.

Refer to Section 7.1 for analysis periods used for analyses and reporting.

5.2 Treatment Regimens

See Section 2.2.

5.3 Populations for Analyses

Populations for analyses are presented in Table 5.3-1.

Table 5.3-1: Populations for Analyses

Population	Description
Enrolled participants	All participants who sign informed consent and are assigned Participant Identification Number. This population is used for all non-PK listings and to summarize study conduct.
Treated participants	Enrolled participants who receive at least 1 dose of study therapy (DCV or SOF). This population is used to summarize pretreatment characteristics, efficacy and on-treatment safety.
Follow-up participants	Treated participants who continue into the LTFU period, as indicated on the end of treatment subject status CRF. This population is used to summarize follow-up safety and duration of virologic response.

6 STATISTICAL ANALYSES

Statistical analyses are performed using the version of UNIX SAS or S-Plus in production, unless otherwise specified.

6.1 General Methods

All summarizes are presented by cohort and total, unless specified otherwise.

Continuous parameters are summarized using univariate statistics, i.e., number of participants (n), mean, standard deviation (SD), median, quartiles, minimum and maximum. Categorical parameters are summarized using counts and percentages, or counts and proportions depending on the endpoint.

In general, all confidence intervals (CIs) are 2-sided with 95% coverage, unless otherwise specified. CIs for binary endpoints are based on exact binomial distribution. CIs for continuous endpoints are based on the normal distribution.

Longitudinal summaries of efficacy, safety, and questionnaire endpoints use pre-defined analysis visit windows.

Laboratory test endpoints are determined from measurements analyzed at both local and central laboratories, and are summarized using both Système International (SI) and US standard units.

Frequencies and percentages of participants with events are presented for the following: relevant protocol deviations; interruptions of study therapy; non-study medications; AEs; laboratory test and ECG abnormalities. Multiple occurrences of the same event are counted once per participant selecting the worst event to summarize, unless specified otherwise.

By-participant listings are provided for select endpoints, and are sorted by cohort, site identifier, and subject identifier. Listings display all events regardless of study period unless otherwise specified. Select listings (e.g., AEs, laboratory tests) display temporal dosing status according to the GBS standard temporal dosing model.¹

Participants who move to another investigative site during the study are classified according to their original investigative site, country and geographic region.

Formats of tables, listings, and graphs are described in the Data Presentation Plan.

6.2 Study Conduct

Relevant protocol deviations are summarized for treated participants. Relevant protocol deviations are those that are programmable and could potentially affect the interpretability of the study results, such as:²

- Certain inclusion or exclusion criteria;
- Incorrect dosing or study treatment assignment;
- Use of prohibited concomitant medications;
- Participants remaining on treatment despite having met specified criteria for withdrawal.

APPENDIX 1 describes the relevant protocol deviations that can be programmed from the database.

6.3 Study Population

6.3.1 Disposition of Participants

6.3.1.1 Pre-Treatment Subject Status, Enrollment, and Accrual

Populations for analyses (see Section 5.3) are summarized with counts only (no percentages) for enrolled participants.

Pre-treatment subject status is summarized for enrolled participants (total only, not by cohort) for the following categories: enrolled, treated, not treated, and the reasons for not being treated (e.g., AE, lost to follow-up, death).

Enrollment at each site by country is summarized for enrolled participants by the following populations (not by cohort): enrolled and treated. Enrollment by age group is summarized analogously. Age group categories are: in utero; preterm newborn (gestational age < 37 weeks); newborns (0 to 27 days); infants and toddlers (28 days to 23 months); children (2 to 11 years); adolescents (12 to 17 years); adults (18 to 64 years); adults (65 to 84 years); adults (≥ 85 years).

Accrual by month and year of initial study therapy is also summarized for treated participants.

6.3.1.2 End of Treatment Subject Status

End of treatment subject status is summarized for treated participants for the following categories: completing the period, not completing the period (including reasons for not completing), continuing to the follow-up period, not continuing to the follow-up period, and not reported (i.e., no subject status data).

A by-participant listing of end of treatment subject status is provided for treated participants.

6.3.1.3 End of Study Subject Status

End of study subject status is summarized for follow-up participants for the following categories: completing the study, not completing the study (including reasons for not completing), and not reported (i.e., no subject status data).

A by-participant listing of end of study subject status is provided for treated participants.

6.3.2 Demographics and Other Baseline Characteristics

Demographics and other baseline characteristics are summarized for treated participants.

Summaries of categorical parameters identify the number and percentage of participants with not reported (i.e., missing) measurements, unless specified otherwise.

For treated participants, the baseline value of a parameter (e.g., laboratory test, HCV RNA, ECG, vital sign, physical measurement, questionnaire) is defined as the last, non-missing, valid value collected or measured on or before the start date of study therapy.

6.3.2.1 Demographics

Demographics are presented in Table 6.3.2.1-1.

Table 6.3.2.1-1: Demographic Characteristics

Parameter (Units)	Type	Categories
Age at Day 1 from IRT (years)	Continuous and categorical	3 to < 6, 6 to < 12, 12 to < 18 years
Age at enrollment (years)	Continuous and categorical	3 to < 6, 6 to < 12, 12 to < 18 years
Gender	Categorical	Male, Female
Race	Categorical	White Black or African American Asian, with the following subcategories:

Table 6.3.2.1-1:	Demographic Characteristics	
		Other
Ethnicity	Categorical	Hispanic or Latino Not Hispanic or Latino
Country by Geographic Region	Categorical	Countries within the following regions, as applicable: Asia (Taiwan) Europe (Germany, Poland, Romania, Spain) Pacific Rim/Oceania (Australia)

If sites from other countries are included or excluded in this study, then the associated geographic regions are redefined accordingly.

A by-participant listing of demographics is provided for enrolled participants.

6.3.2.2 HCV Disease Characteristics and Virologic Resistance at Baseline

HCV Disease Characteristics

HCV disease characteristics at baseline are presented in Table 6.3.2.2-1.

Table 6.3.2.2-1: HCV Disease Characteristics at Baseline

Parameter (Units)	Туре	Categories
HCV RNA (log ₁₀ IU/mL)	Continuous and categorical	$< 800,000, \ge 800,000, < 2,000,000, \ge 2,000,000$ IU/mL
HCV genotype	Categorical	1, 1a, 1b, 2, 3, 4, 5, 6 (example; include subtypes)
Cirrhosis status	Categorical	Present, Absent
IL28B rs12979860 host genotype	Categorical	CC, CT, TT
HCV treatment history status	Categorical	Naive, Experienced

Cirrhosis status is derived as per APPENDIX 1.

HCV treatment experienced participants are defined as those who received any prior non-study anti-HCV treatment, while HCV treatment naive participants are defined as those who did not receive any prior non-study anti-HCV treatment (see APPENDIX 1).

A by-participant listings of baseline disease characteristics is provided for treated participants.

Virologic Resistance at Baseline

NS5A resistance testing at baseline is performed on all participants. NS5A key genotypic substitutions at baseline are summarized as categorical parameters for participants with genotypable baseline isolates in the following populations: (1) treated participants; (2) SVR non-responders, which include virologic failures (see Section 6.5.1.2).

NS5B resistance testing at baseline is performed only for virologic failures. Thus, NS5B key genotypic substitutions at baseline are summarized analogously for SVR non-responders with genotypable baseline isolates.

See APPENDIX 2 for key NS5A and NS5B genotypic substitutions.

6.3.2.3 ECGs, Vital Signs, and Physical Measurements at Baseline

ECGs, vital signs, and physical measurements at baseline are summarized as continuous parameters (see Table 6.3.2.3-1).

Table 6.3.2.3-1: ECGs, Vital Signs, and Physical Measurements at Baseline

Parameter (Units)

ECGs (msec): PR interval, QRS width, QT interval, QTC Bazett's (QTcB), QTc Fridericia's (QTcF)

Vital signs: heart rate (bpm), systolic blood pressure (mmHg), diastolic blood pressure (mmHg), respiration (breaths/min), temperature (°C)

Physical measurements: height (cm), height for age Z score (HAZ), height for age percentile (HAP), weight at Day 1 from IRT (kg), weight (kg), weight for age Z score (WAZ), weight for age percentile (WAP), body mass index (BMI; kg/m²), BMI for age Z score (BMIAZ), BMI for age percentile (BMIAP)

Physical measurement Z scores and percentiles are calculated using the SAS program for the 2000 Center for Disease Control (CDC) Growth Charts (ages 0 to < 20 years).³

6.3.2.4 Laboratory Tests at Baseline

Laboratory test abnormalities at baseline are summarized as categorical parameters using toxicity grades separately for SI and US units. Percentages are based on participants with measurements.

Commonly collected laboratory tests that are graded using the Division of AIDS (DAIDS) Table for Grading the Severity of Adult and Pediatric Adverse Events (2004)⁴ toxicity grades (Grades 0, 1, 2, 3, 4; Grade 1 to 4; Grade 3 to 4) include the following, as applicable:

- Hematology: hemoglobin, platelets, international normalized ratio (INR), white blood cell count (WBC), lymphocytes (absolute; only for Cohort 1 participants > 13 years old), and neutrophils + bands (absolute; ANC);
- Hepatobiliary enzymes and measures of hepatic synthetic function: alanine aminotransferase (ALT), aspartate aminotransferase (AST), alkaline phosphatase, total bilirubin, and albumin;
- Pancreatic enzymes and renal function tests: lipase (colorimetric or turbidimetric) and creatinine;
- Electrolytes: bicarbonate (low), calcium (high and low), phosphate (low), potassium (high and low), and sodium (high and low).

See Protocol Appendix 5 for DAIDS toxicity grades.

In the absence of DAIDS toxicity grades, the following toxicity grade categories are provided for creatinine clearance using the Schwartz formula:

- SI units (mL/s/ m^2): < 0.25 (Grade 4); 0.25 to < 0.50 (Grade 3); 0.50 to < 1.0 (Grade 2); 1.0 to < 1.5 (Grade 1); \ge 1.5 (Grade 0);
- US units (mL/min/1.73 m²): < 15 (Grade 4); 15 to < 30 (Grade 3); 30 to < 60 (Grade 2); 60 to < 90 (Grade 1); ≥ 90 (Grade 0).

General Medical History

A by-participant listing of general medical history is provided for enrolled participants.

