Section 9.8.2.3 Brief Questionnaire/Interim Phone Contact	Added note: Due to the early termination of the study, participants will perform an EOS visit and interim telephone contact will not be necessary after the EOS visit.	[REDACTED]
Section 10.1 Sample Size Determination	Added note: Not Applicable due to the early termination of the study; a total of 5 participants will have been enrolled in the study into Cohort 1.	[REDACTED]
Section 10.3 Statistical Analyses	Added note: With the early termination of this study, previously collected data to address PK, SVR, and select safety assessments (e.g. AEs, laboratory tests, end of treatment subject status) will be reported only within adolescent participants 12 to <18 years of age. Given the small number of subjects enrolled in the study, no statistical analyses will be performed. Genotypic substitution(s) associated with virologic failure and the acceptability and palatability of the DCV formulations will not be reported. Likewise, an interim analysis will not be performed.	[REDACTED]
Section 10.3.2 Resistance Analyses	Added note: These data will not be reported because the prevalence of the relevant RAV varies from 4-10% and as such might not be detected at Baseline in a sample size of 5 participants. As of 18 October 2019, all participants had completed at least 41 weeks of post-treatment follow-up and none had experienced virologic failure.	[REDACTED]
Section 10.3.5.1 Acceptability and Palatability Assessments of Daclatasvir Formulations	Added note: These data will not be reported as only the adult formulation was administered in the study and there is no value to perform an analysis of the adult formulation	[REDACTED]
Section 10.3.6 Interim Analysis	Added note: An interim analysis will not be performed. As only 5 subjects will be enrolled in this study, analyses are not needed to guide dosing for additional participants.	[REDACTED]
Appendix 5	Updated version of DIADS table from December 2004 to July 2017 version 2.1 of DAIDS Table for Grading the Severity of Adult and Pediatric Adverse Events	[REDACTED]

█ [REDACTED]

█ [REDACTED]

█ [REDACTED]

TABLE OF CONTENTS

TITLE PAGE	1
DOCUMENT HISTORY	3
[REDACTED]	[REDACTED]
SUMMARY OF KEY CHANGES FOR REVISED PROTOCOL 01	5
TABLE OF CONTENTS	10
1 SYNOPSIS	13
2 SCHEDULE OF ACTIVITIES	19
[REDACTED]	[REDACTED]
[REDACTED]	[REDACTED]
[REDACTED]	[REDACTED]
[REDACTED]	[REDACTED]
4 OBJECTIVES AND ENDPOINTS	31
5 STUDY DESIGN	31
5.1 Overall Design	31

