10.3.3 Safety Analyses

The frequencies of the following safety endpoints will be presented separately for each study period (on treatment and follow-up) for treated participants by age cohort and total: SAEs; AEs leading to discontinuation of study therapy; AEs by intensity; laboratory abnormalities by toxicity grade.

The Investigators will determine the intensity of AEs. The Investigators' terms will be coded and grouped by system organ class using the latest version of the Medical Dictionary for Regulatory Activities (MedDRA) in production. AEs will be presented by system organ class and preferred term. Presentations will include both non-serious and SAEs, unless specified otherwise. If a participant had an AE with different intensities over time, then only the greatest intensity will be reported for a study period.

Laboratory toxicities will be graded according to the Division of AIDS (DAIDS) of the US National Institutes of Health table for grading the severity of adverse experiences ([December 2004; clarification August 2009]) ([Appendix 5](#)). The laboratory value during the study period with the highest toxicity grade will be reported for each test.

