
Unacceptable Methods of Contraception
 
 • Periodic abstinence (calendar, symptothermal, post-ovulation methods) • Withdrawal(coitus interruptus). • Spermicide only • Lactation amenorrhea method (LAM)

CONTRACEPTION GUIDANCE FOR MALE PARTICIPANTS WITH PARTNER(S) OF CHILD BEARING POTENTIAL.

Male participants with female partners of childbearing potential are eligible to participate if they agree to the following during the treatment and until the end of relevant systemic exposure.

- Inform any and all partner(s) of their participation in a clinical drug study and the need to comply with contraception instructions as directed by the investigator.
- Male participants are required to use a condom for study duration and until end of relevant systemic exposure defined as 5 Days (5 half lives of the study drug) after the end of treatment plus an additional 90 days.
- Female partners of males participating in the study to consider use of effective methods of contraception until the end of relevant systemic exposure, defined as 5 Days after the end of treatment in the male participant.
- Male participants with a pregnant or breastfeeding partner must agree to remain abstinent from penile vaginal intercourse or use a male condom during each episode of penile penetration during the treatment and until 5 Days after the end of treatment.
- Refrain from donating sperm for the duration of the study treatment and until 5 Days after the end of treatment plus an additional 90 days.

COLLECTION OF PREGNANCY INFORMATION

Guidance for collection of Pregnancy Information and outcome of pregnancy on the Pregnancy Surveillance Form is provided in [Section 9.2.5](#) and the Appendix for Adverse Events and Serious Adverse Events Definitions and procedures for Evaluating, Follow-up and Reporting

APPENDIX 5

**DIVISION OF AIDS (DAIDS) TABLE FOR GRADING THE
SEVERITY OF ADULT AND PEDIATRIC ADVERSE EVENTS
PUBLISH DATE: JULY, 2017**

Division of AIDS (DAIDS) Table for Grading the Severity of Adult and Pediatric Adverse Events

**Corrected Version 2.1
July 2017**

**Division of AIDS
National Institute of Allergy and Infectious Diseases
National Institutes of Health
US Department of Health and Human Services**

Table of Contents

Glossary and Acronyms	1
Introduction.....	3
Instructions for Use	4
Major Clinical Conditions.....	7
Cardiovascular	7
Dermatologic	9
Endocrine and Metabolic	10
Gastrointestinal	12
Musculoskeletal	14
Neurologic.....	15

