7.4.4 Laboratory Test Results

Toxicity grades are based on standard values, standard lower limit of normal (LLN), and standard ULN, as applicable. If a laboratory value that is graded as a multiple of the ULN or LLN falls between 2 toxicity grades, then the higher toxicity grade is assigned (e.g., an ALT value that is 2.53 x ULN is classified as Grade 2, not Grade 1).

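### Laboratory grading names the 2004 DAIDS table but points to the July 2017 one; the SAP's own creatinine clearance scale is one grade lower from 15 to < 90 mL/min/1.73 m² on absolute cut-offs, and its SI unit is mislabelled

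*SAP*

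**What the plan says.** **Edition.** Protocol 10.3.3 grades laboratory toxicities by the DAIDS table for "grading the severity of adverse experiences ([December 2004; clarification August 2009", and cites Appendix 5 in the same sentence. The title of Appendix 5 reads "PUBLISH DATE: JULY, 2017", and its cover page calls it corrected version 2.1. SAP 6.3.2.4 names the DAIDS "Table for Grading the Severity of Adult and Pediatric Adverse Events (2004" edition and a few lines later says "See Protocol Appendix 5 for DAIDS toxicity grades".

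**Creatinine clearance.** SAP 6.3.2.4 continues: "In the absence of DAIDS toxicity grades, the following toxicity grade categories are provided for creatinine clearance using the Schwartz formula". It gives one scale in US units (mL/min/1.73 m²) and one in SI units labelled mL/s/m². Protocol Appendix 5, under Chemistries, has a row for low creatinine clearance or eGFR. That row has absolute cut-offs, alternative criteria based on percentage decrease from baseline, an instruction to take the higher grade, and a footnote listing Schwartz among the formulas.

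**Serum creatinine** is also graded: the SAP list includes "lipase (colorimetric or turbidimetric) and creatinine".

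**Reuse.** SAP 6.6.4.1 takes the 6.3.2.4 grades into the on-treatment and follow-up summaries, and SAP 6.6.4 takes them into the listing flags.

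**Between-grade rule.** SAP 7.4.4 assigns the higher grade to a multiple-of-limit value lying between two grades. Its example is "an ALT value that is 2.53 x ULN is classified as Grade 2, not Grade 1".

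**The concern.** The documents name one grading table and point to another. For creatinine clearance the difference changes the reported grade. The reason the SAP gives for using its own scale does not apply to the table in Appendix 5, and the SAP does not say that it departs from DAIDS.

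Laboratory abnormalities by toxicity grade are part of a secondary safety endpoint (Protocol Section 4), and Protocol 10.3 keeps laboratory tests among the data to be reported after early termination. A reader told that DAIDS was used would expect a creatinine clearance of 30 to < 60 in the Grade 3 to 4 row. Under the SAP it is Grade 2. With five participants, one regraded person moves a row by 1/5 = 20 percentage points.

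The SI label is a separate slip. SAP 6.6.4 requires laboratory output separately in SI and US units, so the wrong unit would be carried into the SI output.

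**Working it through.** **Step 1. Absolute cut-offs side by side** (mL/min/1.73 m²; SAP 6.3.2.4 US scale against the Appendix 5 row)

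| Creatinine clearance | SAP grade | Appendix 5 grade | Difference |
|---|---|---|---|
| < 15 | 4 | 4 | 0 |
| 15 to < 30 | 3 | 4 | 1 |
| 30 to < 60 | 2 | 3 | 1 |
| 60 to < 90 | 1 | 2 | 1 |
| ≥ 90 | 0 | none | 0 |

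A scan from 0 to 150 in steps of 0.01 gave a difference of exactly one grade at every value from 15.00 to 89.99 and none elsewhere.

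**Step 2. Percent-decrease criteria.** Appendix 5 also gives Grade 2 for a fall of 10 to < 30%, Grade 3 for 30 to < 50% and Grade 4 for ≥ 50%, and the higher grade counts. After baseline the gap can therefore exceed one grade. For 120 to 80 the fall is 40/120 = 33.3%: SAP Grade 1, Appendix 5 Grade 3. For 120 to 60 the fall is 50%: SAP Grade 1, Appendix 5 Grade 4.

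**Step 3. How much the serum creatinine row already catches.** The Schwartz formula (Protocol 6.2, criterion 3i) is length × k / creatinine. With length and k constant,

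creatinine fold-rise = 1 / (1 − fractional fall in clearance).

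- Clearance falls of 10%, 30% and 50% give 1.11-, 1.43- and 2.00-fold creatinine.
- The Appendix 5 creatinine limits of 1.3-, 1.5- and 2.0-fold (Grades 2, 3 and 4) correspond to falls of 23.1%, 33.3% and 50%.

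If those baseline-relative creatinine criteria are applied, and the ULN criterion is set aside, any fall of ≥ 33.3% is already Grade 3 or 4 on creatinine. That includes every fall from ≥ 90 to < 60, because 90/60 = 1.5. For a baseline of ≥ 60, the Grade 3 to 4 cases missed by both the SAP scale and the creatinine row are:

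| Case | Example | Fall | Fold | SAP clearance | Creatinine row | Appendix 5 clearance |
|---|---|---|---|---|---|---|
| (a) baseline 60 to < 90, to below 60, fall < 33.3% | 75 to 55 | 26.7% | 1.36 | 2 | 2 | 3 |
| (b) fall 30 to < 33.3%, ending at ≥ 60 | 110 to 75 | 31.8% | 1.47 | 1 | 2 | 3 |

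This overlap is not assured: SAP 7.4.4 bases grades on standard values and normal limits and does not mention baseline-relative criteria.

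**Step 4. SI unit.** The SAP cut-offs are 0.25, 0.50, 1.0 and 1.5. Dividing 15, 30, 60 and 90 mL/min/1.73 m² by 60 gives exactly these numbers in mL/s/1.73 m². In true mL/s/m² a further division by 1.73 gives 0.145, 0.289, 0.578 and 0.867. Read as labelled, 1 mL/s/m² = 60 × 1.73 = 103.8 mL/min/1.73 m². A value of 100 would then be 100/103.8 = 0.963 mL/s/m²: Grade 2 in SI, Grade 0 in US units. The same label stands in SAP 6.6.4.3 and in SAP Appendix 1, criterion 3i. Under a literal reading of 3i, a participant would be flagged only if all pre-treatment values were below 103.8.

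**Step 5. Other signs of an older table.** In Appendix 5, ALT Grade 1 is 1.25 to < 2.5 × ULN and Grade 2 is 2.5 to < 5.0 × ULN. A value of 2.53 × ULN is therefore plainly Grade 2, and the SAP 7.4.4 example is no longer a between-grades case. The SAP also grades lymphocytes only in Cohort 1 participants above 13 years, whereas Appendix 5 grades them above 5 years.

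**The case against.** The SAP names the 2004 table just before it says a DAIDS grade is absent, so it may mean absent from that edition. The SAP still describes 30 participants, three cohorts and interim analyses, and the protocol's change summary records "Updated version of DIADS table from December 2004 to July 2017 version 2.1" for Appendix 5. On that inference the SAP and the appendix agreed when the SAP was written, and the SAP was simply not realigned. This is the probable cause, and it is why the claim is limited to the table now referred to. It does not remove the conflict: Protocol 10.3.3 contradicts its own appendix whatever the SAP's date.

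The effect is narrow, and this stands. There are five participants and no statistical analyses. Exclusion criterion 3i bars clearance below 60, listings show every value, and SAP 6.6.4.3 counts confirmed on-treatment values below 60. Protocol 6.4.1 judges eligibility on the latest pre-dose result, so a baseline below 60 would need a deviation or a Day 1 sample reported after dosing. It is possible but unlikely.

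Adopting the 2017 table would also regrade data collected before this revision, since by 18 October 2019 everyone had at least 41 weeks of post-treatment follow-up. That is a fair reason to date and document the change. It is not a reason to leave two editions in force.

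Finally, the ALT example still yields the right grade, the SI slip is harmless unless read literally, and the lymphocyte limit concerns only ages 12 to 13 in Cohort 1, with no sign that anyone of that age was enrolled. All three are editorial.

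**Conclusion.** The concern holds. Both documents name an edition that is not the one in Appendix 5, and the SAP's reason for its own creatinine clearance scale is untrue of that appendix. The scale is one grade lower from 15 to < 90 mL/min/1.73 m² on absolute cut-offs, and the gap can be wider after baseline once percentage falls count. The SI unit lacks the factor 1.73.

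The overlap result in Step 3 assumes constant height and k and that the July 2017 baseline-relative creatinine criteria are applied. Nothing is claimed about the content of the 2004 table. The point should be corrected because it alters a reported secondary safety endpoint as specified, but no participant is known to be affected.

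**What to change.** 1. Name one DAIDS edition in Protocol 10.3.3 and SAP 6.3.2.4 that matches Appendix 5. July 2017 is the consistent choice.
2. In SAP 6.3.2.4, delete the claim that DAIDS grades are absent. Then either (a) use the Appendix 5 creatinine clearance row and state in SAP 7.4.4 that its baseline-relative criteria and higher-grade rule apply, or (b) keep the SAP scale as a declared and justified departure from DAIDS.
3. In SAP 7.4.4, say whether baseline-relative criteria apply to serum creatinine, and replace the ALT example with one that fits the chosen edition.
4. Correct the SI unit to mL/s/1.73 m² in SAP 6.3.2.4, SAP 6.6.4.3 and SAP Appendix 1 (3i).
5. Align the lymphocyte age limit with the chosen edition.

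The cost is wording in one protocol section and four SAP places, plus a small change to the grading program under option (a). Graded counts may rise slightly. Record it as a dated correction, before database lock if the lock has not occurred; the documents give no lock date.
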